9.3. Reporting period

As a minimum, SAEs will be documented and reported in accordance with the procedures described above from the date of first administration of IMP until the end of the IMP treatment period. Any collection of SAEs beyond the treatment period will be specific to the intervention under investigation and the rationale for this will be described within the specific IMP appendix of the protocol. SUSARs must still be reported in an expedited manner irrespective of how long after administration the reaction occurred.

9.4. Reporting procedure

9.4.1. Adverse events

Specified adverse events will be reported directly into the eCRF for all participants, including those randomised to receive standard care. The data monitoring committee will review reported adverse events across all arms of the trial on a regular basis to monitor for any safety signals. Care home staff will be trained to report any adverse events that meet the criteria for a SAE and which are not excluded from requiring reporting via the SAE reporting process outlined in section 9.4.2.

9.4.2. Serious adverse events

SAEs will be entered into a trial SAE form within the eCRF by a member of care home staff or GP directly responsible for the care of the participant. The person completing the report will include sufficient details of the event to facilitate the assessment of relatedness by a member of the national team of medically qualified Principal Investigators. Should a participant's general practitioner become aware of an SAE during the reporting period, they may report the event via the same process. A Principal Investigator will review the information in the SAE report and will liaise with the reporting care home or GP to obtain further information where necessary.

On receipt of an SAE, seriousness and causality will be determined independently by the PI. An SAE judged by the PI to have a reasonable causal relationship with the trial treatment will be regarded as a SAR. The PI will also assess all SARs for expectedness against the Reference Safety Information for the IMP. If the serious event is unexpected (i.e. is not defined in the protocol as an expected event) it will be classified as an unexpected SAR (SUSAR). Expedited reporting for SUSARs will be carried out as detailed in section 9.5.2.

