It is expected that participants in the trial will have a range of underlying co-morbidities and so infection with SARS-CoV-2 may lead to serious and significantly life-threatening conditions, which are outcomes for this trial. Safety reporting in the trial will therefore focus only on those events that could be related to the trial medication, are serious in nature (according to the SAE definition below) and are unexpected (either the event itself or in severity) according to the reference safety information (RSI) for the IMP. Further information regarding the RSI can be found in the appendix for each IMP. Once an intervention has been identified by the NIHR Prophylaxis Oversight Group, the risk profile of the IMP will determine any further safety reporting requirements beyond those described below. These will be detailed within the IMP appendix.

Trial	Prophylactic therapy in care homes trial	Protocol	Final v1.0	date:	13-May-2021	Page:	28 of 44
name:	U1111-1265-4068	version:					

The known or anticipated side effects of the IMPs are listed in the IMP appendices. Side effects will be apparent to residents with capacity and to care home staff. In particular, care home staff know their residents and their medical problems intimately and so can see deterioration very early; indeed side effects are likely to be identified earlier and potentially more frequently than they would be in people living in their own home. We will train care home staff to look for side effects through training at the site initiation visit and in videos available for download via the trial website. If side effects are apparent, care home staff may inform the resident's GP. All side effects will be entered into the trial database on a weekly basis by care home staff. Serious adverse events, hospitalisation and death will all be reported in real time via the trial database for review by the relevant principal investigator, for independent review by the medical adjudicator and Data Monitoring Committee, and for forwarding to the competent authority within the standard reporting periods relevant to SAEs, SARs and SUSARs.

A serious adverse event that is not expected against the RSI and considered to be related or suspected to be related to the IMP is classed as a Suspected Unexpected Serious Adverse Reaction (SUSAR) and requires expedited reporting as per the clinical trials regulations.

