9.1. Adverse events

Adverse events are common in this population due to the range of underlying comorbidities, therefore events that are deemed expected for this population (see section 9.2.1) will not be reported. Care home staff will report pre-specified adverse events (based on treatments under investigation for any given comparison group within the platform – further details are specified within the relevant IMP appendices) for all residents directly via the eCRF

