9.2.1. Events that do not require reporting

The following events are frequent in care homes and will not be reported as AEs or SAEs:

Trial	Prophylactic therapy in care homes trial	Protocol	Final v1.0	date:	13-May-2021	Page:	29 of 44
name:	U1111-1265-4068	version:					

- Agitation
- Allergic reaction (not related to trial medication)
- Anorexia, loss of appetite
- Bowel obstruction
- Bruising, ecchymoses
- Confusion
- COVID-19 (part of the primary outcome)
- Delirium
- Dehydration
- Diarrhoea, with/without norovirus/Clostridium difficile
- Fall with injury, with/without fracture
- Heart failure, volume overload
- Hypoglycaemia
- Hypotension
- Incontinence (urinary, bowel)
- Medication (non-trial) error
- Nursing care, missed
- Pressure ulcer
- Respiratory distress/failure (non-COVID-19)
- Respiratory infection (non-COVID-19)
- Sepsis, bacteraemia
- Skin tear, abrasion, breakdown
- Suicide, attempted suicide, self-harm
- Surgical/procedural site infection
- Urinary tract infection, with/without catheter
- Venous thromboembolism
- Vomiting, with/without norovirus
- Any event listed in the IMP appendices

Similarly, diagnoses present at baseline (including any worsening of that condition) and known comorbidities will not be reported. Known side effects for the intervention(s) will be listed in the relevant IMP appendix.

If any of the above lead to hospitalisation or death, then they will comprise part of the primary outcome.

Trial	Prophylactic therapy in care homes trial	Protocol	Final v1.0	date:	13-May-2021	Page:	30 of 44
name:	U1111-1265-4068	version:					

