9.5. Expedited reporting

9.5.1. Reference safety information (RSI)

RSI is a list of medical events that defines which events are expected for the IMP within a given trial and thus determining which SARs require expedited reporting.

For the purpose of this trial, the Reference Safety Information is referred to in the IMP appendices.

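### The protocol gives conflicting tests of expectedness, and its list of events exempt from reporting has no general exception for serious events suspected to be related to the IMP

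*Protocol*

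**What the plan says.** The RSI is the declared standard. Protocol 9.5.1 says "RSI is a list of medical events that defines which events are expected for the IMP within a given trial" and adds that it determines which SARs need expedited reporting. The opening text of section 9 defines a SUSAR as "A serious adverse event that is not expected against the RSI and considered to be related or suspected to be related to the IMP". In 9.4.2 the PI is instructed: "The PI will also assess all SARs for expectedness against the Reference Safety Information for the IMP". SAP 8.1 uses the same standard.

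The next sentence of 9.4.2 words the test differently: "If the serious event is unexpected (i.e. is not defined in the protocol as an expected event) it will be classified as an unexpected SAR". Section 14.9 has a further version for the event adjudicators. Their SUSAR category leaves out trial outcomes as well as expected events given in the protocol or its appendices.

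On reporting, 9.1 says that "events that are deemed expected for this population (see section 9.2.1) will not be reported", and 9.2.1 opens with "The following events are frequent in care homes and will not be reported as AEs or SAEs". Sections 9.2 and 9.4.1 repeat the exclusion for SAEs. Section 9.2.1 also excludes diagnoses present at baseline, including their worsening.

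**The concern.** Expectedness for a drug and background frequency in a population are different things. The first decides whether a related serious event needs expedited reporting. The second only says how often the event occurs anyway. The protocol uses the word expected for both, and the sentence that assigns SUSAR status does not say which it means.

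The 9.2.1 list acts earlier, at the point of reporting. If a listed event never produces an SAE form, nobody is clearly charged with asking whether the drug caused it. At stake are the assessment of a new serious reaction that looks like an ordinary care-home event, its expedited reporting under 9.5.2, and the completeness of the SAE, SAR and SUSAR summaries in SAP 8.1. At 1:1 allocation about 3,200 residents per comparison are in active-treatment homes (6,400 / 2).

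**Working it through.** No power or error-rate arithmetic applies. The check sets the passages side by side and counts the list.

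**Step 1: the tests of expectedness.**

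- Section 9 opening, 9.5.1, SAP 8.1 and the RSI sentence of 9.4.2: the IMP's RSI.
- The SUSAR sentence of 9.4.2: an event that "is not defined in the protocol as an expected event". It names neither the RSI nor 9.2.1.
- Section 14.9: neither a trial outcome nor an expected event in the protocol or its appendices.

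The bracket in 9.4.2 has two possible readings. It can mean the RSI, since "the Reference Safety Information is referred to in the IMP appendices" and those appendices belong to the protocol. It can also mean 9.2.1, since 9.1 applies the word expected to that list. Section 14.9 names the protocol and its appendices as two sources, which lends some support to the second reading. On that reading an event absent from the RSI could count as expected because it is common.

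**Step 2: the count in 9.2.1.**

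- Bullets: 28. The last refers to the IMP appendices and is set aside, leaving 28 - 1 = 27 named events.
- With a trial-medication qualifier: 2 (allergic reaction, non-trial medication error).
- COVID-19, listed because it is part of the primary outcome: 1.
- Without any exception for relatedness: 27 - 2 - 1 = 24.

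The 24 include venous thromboembolism, sepsis, respiratory failure, heart failure, hypoglycaemia and bowel obstruction. The qualifier on allergic reaction shows that the need was recognised once but not applied to the list.

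**Step 3: tracing an example.** Take a venous thromboembolism that is serious, suspected to be drug-related and absent from the RSI.

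- *Under 9.2, 9.2.1 and 9.4.1:* it is not reported as an SAE. Section 9.4.2 has the PI determine causality on receipt of an SAE, so that step is not triggered.
- *If it leads to hospitalisation or death:* the section 9 opening has it reported in real time for PI review, while 9.2.1 counts it in the primary outcome. In 14.9 it is then an outcome, which the wording of the adjudicators' SUSAR category leaves out.
- *If it is serious on another criterion and managed in the home:* the hospitalisation and death route does not apply. What remains is the weekly entry of side effects in the section 9 opening, which conflicts with 9.1 and 9.2.1.

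**The case against.** The strongest reply is that the RSI governs. It is named in four places, one of them immediately before the disputed sentence, and the bracket can be read as the RSI held through the IMP appendices. A reader might infer that the care-home list replaces the RSI, or that following 9.4.2 and 14.9 yields no SUSARs for listed events. The documents do not support either inference: 9.4.2 requires RSI assessment of every SAR, and its bracket does not cite 9.2.1.

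A reader might also infer that the DMC and regulator would see nothing. That too goes beyond the text. Section 9 has SAEs, hospitalisation and death reported in real time to the PI, the adjudicator and the DMC, with onward reporting to the competent authority. Adjudicators review outcome events as well as SAEs. Cause-specific admission and mortality are collected, and SAP section 3 gives the DMC results by arm.

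These replies stand against the stronger readings but do not remove the problem. The section 9 text contradicts 9.2 and 9.2.1 instead of overriding them. The bar in 14.9 on downgrading SUSARs protects only events already classed as SUSARs. Outcome comparisons by arm are not an individual causality assessment. Finally, 24 of 27 counts list items and not risk: some, such as skin tears or missed nursing care, are unlikely drug signals.

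**Conclusion.** The point holds as an inconsistency that is wrong as written. It has two parts: conflicting tests of expectedness (9.4.2 and 14.9 against section 9, 9.5.1 and SAP 8.1), and a reporting exclusion with no relatedness exception for 24 of 27 named events or for worsening of baseline diagnoses. The second is the more direct route to a missed SUSAR, because it acts before anyone assesses expectedness.

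The conclusion is that a serious, suspected-related listed event may go unassessed if staff follow the exclusion literally, not that it will. Literal use is plausible: section 1.2.1.1 puts 72% of care homes in the group without nursing, which have no registered healthcare professionals in their core staffing. No event rate can be attached, because the documents give none. The IMP appendices were not available, so their RSI content and any added reporting requirements, which section 9 allows, could not be checked. They could narrow the gap for a given IMP.

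**What to change.** 1. In 9.4.2 and 14.9, define unexpected solely by the RSI for the IMP.
2. In 14.9, remove the exclusion of outcomes from the SUSAR definition. Otherwise a related, unexpected hospitalisation or death stays outside it even after the first change.
3. Apply one qualifier, not suspected to be related to trial medication, to the whole 9.2.1 exclusion, including worsening of baseline diagnoses.
4. Reconcile 9.2, 9.2.1 and 9.4.1 with the opening of section 9, so that it is clear which reports reach the PI for causality assessment.

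Relatedness stays with the PI, as 9.4.2 provides. Staff or GPs need only a suspicion to send a serious listed event on an SAE form, so they are not asked to settle causality.

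The cost is a few wording changes, a line in the care-home training and a modest number of extra SAE forms. No new standard is introduced: the RSI test and the relatedness qualifier are both already in the protocol.

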9.4.3. Provision of follow-up information

Only SARs will be followed-up to resolution.

9.5. Expedited reporting

9.5.1. Reference safety information (RSI)

RSI is a list of medical events that defines which events are expected for the IMP within a given trial and thus determining which SARs require expedited reporting.

For the purpose of this trial, the Reference Safety Information is referred to in the IMP appendices.

9.5.2. Suspected Unexpected Serious Adverse Reactions (SUSARs)

The PI will report events categorised as a SUSAR immediately to the Sponsor.

Trial	Prophylactic therapy in care homes trial	Protocol Final v1.0	date:	13-May-2021	Page:	31 of 44
name:	U1111-1265-4068	version:				

For fatal or life-threatening SUSARs, the Sponsor will ensure expedited reporting to the Medicines and Healthcare products Regulatory Agency (MHRA) and Research Ethics Committee (REC) within 7 days. Any additional relevant information will be provided within an additional 8 days of the report.

For non-fatal or non-life-threatening SUSARs, the Sponsor will ensure expedited reporting as soon as possible but no later than 15 days.

9.5.3. Adverse events

The Sponsor, MHRA and REC will be notified immediately if a significant safety issue is identified by the DMC during the course of the trial.

9.5.4. Investigators

Details of all SUSARs and any other safety issue which arises during the trial will be reported to Principal Investigators, GPs and care homes.

9.6. Data Monitoring Committee (DMC)

The independent DMC will act in accordance with the DMC charter. The DMC will review safety data captured through the reporting of adverse reactions at regular intervals throughout the trial, in addition to reported SAEs in order to monitor for any safety signals.

9.7. Adjudication of SAEs

A team of blinded independent adjudicators will carry out a consistency review on reported events to ensure accurate and complete reporting. Adjudicators will communicate directly with PIs where any inconsistencies are identified.

10. Data Handling and Record Keeping

10.1. Source Data

In order to allow for the accurate reconstruction of the trial and clinical management of the participant, source data will be accessible and maintained.

Data will be collected either directly from the participant or care home staff and uploaded onto a secure database. Source documents shall be filed at the care home and may include but are not limited to, current medical records, laboratory results and records. An eCRF may also completely serve as its own source data. Only trial staff as listed on the Delegation Log shall have access to trial documentation other than the relevant regulatory authorities permitted to have access.

10.2. CRF Completion

Data reported on each electronic Case Report Form will be consistent with the source data and any discrepancies will be explained. Staff delegated to complete eCRFs will be trained to adhere to relevant aspects of GCP associated with data entry.

10.3. Data Management

Arrangements for data handling will be specified in the DMP. This will include the agreed validation specification which will validate data for consistency and integrity as it is entered. Additional manual

Trial	Prophylactic therapy in care homes trial	Protocol Final v1.0	date:	13-May-2021	Page:	32 of 44
name:	U1111-1265-4068	version:				

and electronic reviews may also be conducted, and data queries / clarifications may arise from such reviews.

Data will be held on secure servers. These servers are located within The University of Nottingham data centres, which are managed and monitored 24/7. Security is both physical (secure limited access) and electronic (behind firewalls, access via user accounts (username and password) on encrypted connections,

restricted access – e.g. care home users only have access to their care home's data, and by user type/role). All access and data transactions will be logged in a full audit trail.

Data collected using the eCRF will be transferred from the University of Nottingham to the Trusted Research Environment (TRE) at the University of Dundee's Health Informatics Centre, where it will be linked with participant data from routine sources (GP data, SARS-CoV-2 testing data, hospital data, mortality statistics). Linked data in the TRE will be processed by data manager(s) at the University of Nottingham, via secure remote access, in preparation for analyses. MAR sheets from care homes and Summary Care Records (SCRs) from GPs will be uploaded to the PROTECT-CH secure vault. The PROTECT-CH vault is a secure encrypted data store, separate to the trial database. The secure vault will be accessed by the Principal Investigators (PIs) to check participant eligibility.

10.4. Archiving

In compliance with the ICH:GCP guidelines, regulations and in accordance with the University of Nottingham Research Code of Conduct and Research Ethics, the Chief or local Principal Investigator and care home manager will maintain all records and documents regarding the conduct of the trial. These will be retained for at least 7 years or for longer if required. Participants' medical files should be retained in accordance with applicable legislation and in accordance with the maximum period permitted by the hospital, institution or private practice. Research data sets for analyses will be retained indefinitely.

The Trial Master File and trial documents held by the Chief Investigator on behalf of the Sponsor shall be finally archived at secure archive facilities at the University of Nottingham. This archive shall include all trial databases and associated meta-data encryption codes. No documents shall be destroyed until the minimum retention period has passed and the Sponsor has agreed to the destruction.

10.5. Site Set-up and Initiation

All participating care home managers and Principal Investigators will be asked to sign trial agreements. All members of care home staff facilitating the trial will also be required to sign a trial delegation log. Prior to commencing recruitment all sites will undergo a process of initiation and will have completed essential GCP and trial training. The NCTU must be informed immediately of any change in the care home research team.

Trial	Prophylactic therapy in care homes trial	Protocol Final v1.0	date:	13-May-2021	Page:	33 of 44
name:	U1111-1265-4068	version:				

11. Quality Control and Quality Assurance

11.1. Monitoring

11.1.1. On-site Monitoring

It is not anticipated that there will be any on site monitoring unless triggered by central monitoring checks and it is feasible to conduct these.

11.1.2. Central Monitoring

The NCTU will be in regular contact with the care homes to check on progress and address any queries that they may have. The trial team will check incoming consent forms, Case Report Forms for compliance with the protocol, data consistency, missing data and timing. Care homes will be asked for missing data or clarification of inconsistencies or discrepancies.

11.1.3. Protocol violations

Treatment compliance will be recorded within the REDCap database. Protocol non-compliance outside those recorded in the eCRF will be recorded and reported on a violation form within the database. All instances of non-compliance reported on the violation form will be reviewed by NCTU and where believed to constitute a protocol violation or a potential serious breach will be further investigated. Violations and serious breaches will be investigated as per the appropriate NCTU SOPs and escalated where necessary to the Sponsor and REC/MHRA.

The following will be considered protocol violations and will lead to retraining of the relevant care home:

- Treatment without consent
- Treatment but ineligible
- Non-reporting of primary outcome measures
- Non-reporting of serious adverse events

11.2. Audit and Inspection

The Principal Investigators and care home managers will permit trial-related monitoring, quality checks, audits, ethical reviews, and regulatory inspection(s) at their site, providing direct access to source data/documents. The Principal Investigator and care home managers will comply with these visits and any required follow up.

12. End of Trial Definition

The key timings for each comparison are:

- End of treatment: 42 days
- Primary outcome based on routine national data: 60 days
- Clinical outcomes based on data from care homes: 60 days
- End of follow-up based on routine national data: 120 days
- End of trial: Once last resident has reached 120 days and data cleaned and analysed.

Trial	Prophylactic therapy in care homes trial	Protocol Final v1.0	date:	13-May-2021	Page:	34 of 44
name:	U1111-1265-4068	version:				

The end of the scheduled treatment phase is defined as the date of the last follow-up visit of the last participant. The end of individual comparisons within the platform will be the date of the final data extraction from NHS Digital. This will allow sufficient time for the completion of protocol procedures, data collection and data input. The NCTU will notify the MHRA and REC that the trial has ended within 90 days of the end of trial. Where the trial has terminated early, the NCTU will inform the MHRA and REC within 15 days of the end of trial. The NCTU will provide them with a summary of the clinical trial report within 12 months of the end of trial.

13. Statistical Considerations

